## 9. Research Methods

### 9.1. Study Design

The study is based on data from the nationwide health and administrative registers from Denmark and Sweden, covering country populations of approximately 5.8 million and 10.2 million people, respectively. It is a longitudinal, non-interventional, population-based, register-based cohort study of adolescents and adults with AD exposed to upadacitinib or other select systemic AD treatments, identified in the Danish and Swedish nationwide registers.

Importantly, labelling changes following Article 20 procedure are likely to result in substantial differences in baseline characteristics of patients initiating upadacitinib and those initiating other systemic treatments. Therefore, initial in-depth descriptive analyses will be conducted to assess comparability across treatment cohorts and inform the design (including selection of suitable comparator/s) of subsequent analyses.

The select systemic AD treatments (including biosimilars) evaluated as potential comparator treatments in the study are:

- Azathioprine
- Ciclosporin
- Dupilumab
- Methotrexate
- Mycophenolate mofetil

ATC codes and procedure codes for the comparator treatments are listed in Annex 3. Additional Information, [Table 3.2](#). Additional upcoming marketed AD treatments may become relevant as comparator treatments as the study progresses. Therefore, the list may be extended to cover

other available and approved AD treatments in Sweden and Denmark during the study period. Final codes and definitions will be specified in the Statistical Analysis Plan (SAP) before data extraction for interim analysis and final analysis.

A *new user*, active comparator design will be used to address the objectives of the study. *New user* is defined as not having used that specific drug substance in the year (12 months, 365 days) before the first eligible treatment.

The first dispensed prescription/administration date of upadacitinib or one of the comparator treatments within the study period (see definition in Section 9.2.2. ), will be defined as the *index date*.

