To reduce inflammation in the skin, either pimecrolimus or tacrolimus can be used for topical treatment. They are calcineurin inhibitors that affect inflammatory dendritic epidermal cells and are recommended as second line treatment due to safety reasons [2]. When using anti-inflammatory treatments, combined therapy with emollients should be used. In rare instances oral corticosteroids may be used for the treatment of exacerbation of AD [2]. For very severe cases of AD, cyclosporin A may be used [2]; however, there are side effects including renal toxicity that may lead to hypertension and renal impairment. Another drug sometimes used for severe AD is azathioprine. However, side effects include myelo-suppression, hepatotoxicity, gastrointestinal disturbances, increased risk of infections and possibly skin cancer.

More recently, subcutaneous, oral and topic biologic drugs have been introduced for clinical use in AD. In 2017, the monoclonal antibody dupilumab was approved in the US and EU for adults with moderate to severe AD. Dupilumab binds to interleukin-4 (IL-4) receptors which are involved in signaling pathways relevant for the development of AD [16]. Abrocitinib was approved for adults with moderate to severe AD in the EU in December 2021. Moreover, additional drugs may come to be introduced to the market (e.g., crisaborole, nemolizumab) [17, 18].

Upadacitinib is an oral selective and reversible inhibitor of JAK1. Upadacitinib doses of 15 mg and 30 mg are approved to be used in the EU for treatment of adults with moderate to severe AD. Upadacitinib 15 mg is approved to be used in the EU for treatment of adolescents with moderate to severe AD who weigh 30 kg or over. Following the procedure under Article 20 of Regulation (EC) No 726/2004 (concluded 10 March 2023), upadacitinib recommended use and doses have been changed. Upadacitinib 15 mg is approved to be used in the EU for treatment of elderly patients  $\geq 65$  years of age or patients with risk factors for malignancy, major adverse cardiovascular events (MACE) or venous thromboembolic events (VTEs). In addition, upadacitinib should only be used, if no suitable alternatives are available, in patients 65 years of age or older, in patients with history of atherosclerotic cardiovascular disease or other cardiovascular risk factors and in patients with malignancy risk factors.

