## 9.2. Setting

### 9.2.1. Source Population, Study Population and Study Cohort

The *source population* will be all individuals with at least one diagnosis of AD (ICD-10 code L20) as registered in the Danish and Swedish patient registers since 1998 (the year when ICD-10 was fully implemented in both countries).

To be eligible for inclusion into the *study population* and the *study cohorts* individuals must:

- have a recorded diagnosis of AD
- have at least one dispensed prescription/administration of upadacitinib or one of the select systemic AD treatments within 12 months from the AD diagnosis during the *study period* (see definition in Section 9.2.2. )
- be a *new user* of either upadacitinib or one of the select systemic AD treatments at *index date*
- be  $\geq 12$  years old at the *index date*
- have at least 12 months' continuous residency in the respective country (Denmark or Sweden) prior to the *index date*
- For the potential comparator cohorts, have at least one dispensed prescription/administration of another systemic AD treatment before *index date*

The following exclusion criteria apply to the study population:

- Individuals who used other JAK inhibitors (e.g. tofacitinib, baricitinib, abrocitinib) at any time (all available lookback time) before the *index date* will be excluded

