### 9.2.2. Study Period

The *study period* ranges from first authorization date of upadacitinib for the treatment of AD in Denmark and Sweden (23 August 2021) until 31 December 2031.

Individuals initiating one of the treatments under study will be included through the whole *study period*. To allow for at least 5 years follow-up time for malignancy excluding NMSC and NMSC, for these outcomes the population will be restricted to individuals included up until 31 December 2026.

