**9.7.2.1. Sensitivity Analysis and Subgroup Analysis**

Sensitivity analyses for all safety outcomes will be performed among individuals in the study population with no prior use of any of the other systemic AD treatments within 12 months from *index date*. Sensitivity analyses with 0- and 6-months lag time for malignancy outcomes will be conducted.

In addition, subgroup analyses will be performed by upadacitinib dose, age group, relevant risk factors (e.g., malignancy, VTE, and MACE) and disease histories as listed in the secondary objectives.

Details on the sensitivity and subgroup analyses for all safety outcomes will be described in the SAP.

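### The 365-day same-substance rule makes upadacitinib starters nearly all first-ever users but lets comparator cohorts include people restarting an old drug, whom the listed analyses do not identify

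*Protocol*

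**What the plan says.** Section 9.1 adopts a new-user, active-comparator design. A new user "is defined as not having used that specific drug substance in the year (12 months, 365 days) before the first eligible treatment", and section 9.2.1 makes this status at the index date a condition of entry for every cohort. The index date is "The first dispensed prescription/administration date of upadacitinib or one of the comparator treatments within the study period", so it is the first fill in the period and not the first ever. Under section 9.2.2 the period "ranges from first authorization date of upadacitinib for the treatment of AD in Denmark and Sweden (23 August 2021) until 31 December 2031".

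Section 7 describes older drugs among the candidate comparators. On ciclosporin it says "For very severe cases of AD, cyclosporin A may be used", it also mentions azathioprine, and on dupilumab it says "In 2017, the monoclonal antibody dupilumab was approved in the US and EU for adults with moderate to severe AD".

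Three other provisions deal with treatment history:
- Comparator patients must "have at least one dispensed prescription/administration of another systemic AD treatment before" the index date (section 9.2.1).
- Users of other JAK inhibitors are excluded if the use occurred "at any time (all available lookback time) before the" index date (section 9.2.1).
- A sensitivity analysis is restricted to individuals "with no prior use of any of the other systemic AD treatments within 12 months from" the index date (section 9.7.2.1).

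**The concern.** A new-user design starts follow-up at first exposure in each arm, so that early harms are counted and patients who already tolerated the drug are not mixed with those who have never taken it. Here one rule produces two kinds of cohort: close to pure first exposure for upadacitinib, and an unknown mixture of first exposure and re-exposure for the comparators.

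Someone who returns to a drug has come through at least one earlier course. If that course removed people prone to early events, such as liver injury or infection, the comparator rate would be lowered. If restarters have longer or more severe disease, or carry earlier exposure to the same immunosuppressant, the comparator rate could be raised. Without knowing who the restarters are, the analysis cannot tell either effect from a difference between drugs. The comparability assessment, itself a primary objective, would miss one way in which the cohorts differ.

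**Working it through.** **1. Dates.** Upadacitinib indexing starts on 23 August 2021, its AD authorisation date. Earlier use could only be off-label or for another indication, so nearly all its starters are first-ever users. For a comparator patient indexed on that same day, the 365-day rule looks back to 23 August 2020. Dupilumab use between its 2017 approval and that date is ignored, a window of 2.6 years (from 31 December 2017) to 3.6 years (from 1 January 2017). For drugs in use before dupilumab the window is longer.

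**2. A patient who qualifies.** Methotrexate in 2018–2019, dupilumab from 2020 with the last fill before 23 August 2021, methotrexate again in 2022. The 2022 fill is the first study drug in the period, methotrexate has been absent for more than 365 days, and dupilumab meets the prior-systemic condition. If the AD-diagnosis and residency conditions are also met, this person enters as a new methotrexate user. If dupilumab ran past 23 August 2021, the literal index date would be a dupilumab fill by a current user, and the person would fail the new-user condition.

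**3. A limit on the number of restarters.** Because the index is the first fill in the period, earlier use of the same substance must predate 23 August 2021. A restarter indexed on 23 August 2026 would have been off the drug for at least 5 years. On this reading restarters are likely to be concentrated in the early accrual years.

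**4. Does anything else catch them?**

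| Provision | What it covers | Same drug used more than 1 year earlier |
|---|---|---|
| Prior-treatment condition, 9.2.1 | A different systemic drug | Not excluded |
| Unlimited look-back, 9.2.1 | Other JAK inhibitors only | Not searched |
| Medication covariates, 9.3.3 and Table 1 | In general 1 year; the AD-treatment item leaves out the study drugs | Not captured as listed |
| Sensitivity analysis, 9.7.2.1 | Other systemics, 12 months | Not removed |
| Outcome history exclusions, Table 3.3 | Earlier outcome events, in all cohorts | Not identified |

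**5. Illustrative size.** The study-size section is redacted, so the plan has no figure to reproduce. Let s be the restarter share in the comparator cohort and r their event rate relative to first-time starters of the same drug. The protocol gives neither, so both are assumptions. With a true hazard ratio of 1, the comparator rate is multiplied by (1 − s) + s·r, and the observed ratio is about 1 / (1 − s + s·r).

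| s | r = 0.5 | r = 0.8 | r = 1.25 | r = 1.5 |
|---|---|---|---|---|
| 10% | 1.05 | 1.02 | 0.98 | 0.95 |
| 20% | 1.11 | 1.04 | 0.95 | 0.91 |
| 30% | 1.18 | 1.06 | 0.93 | 0.87 |
| 40% | 1.25 | 1.09 | 0.91 | 0.83 |

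These values hold r over the whole of follow-up, whereas depletion of susceptible patients acts mainly early. If r = 0.5 applies only to the first 0.5 year of 5 years at constant hazard, the average is (0.5 × 0.5 + 4.5 × 1) / 5 = 0.95. Then s = 20% gives 1 / (1 − 0.20 × 0.05) = 1.01 and s = 30% gives 1 / (1 − 0.30 × 0.05) = 1.02. The effect would be larger for outcomes whose events cluster soon after starting.

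**The case against.** The strongest reply is that the consequence is speculative. The protocol gives no restart share and no restarter risk. Section 7 does not describe repeat courses. People off a drug for over a year may have stopped because they did not tolerate it, so even r < 1 is uncertain. All of this stands, and it means the tables above are not estimates.

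A reader might infer that upadacitinib will look worse for early events and better for malignancy. The documents do not support a direction. For malignancy in particular, earlier immunosuppressant exposure is not confined to the comparators: section 9.7 expects high-risk upadacitinib users to be more likely to have failed other therapies, and comparator patients must already have had another systemic drug. That exposure remains in both arms whichever look-back is used.

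Section 9.2.1 also ties treatment to within 12 months of the AD diagnosis. If that means the first diagnosis, earlier courses given for AD would be uncommon, but the text does not say which diagnosis counts.

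Comparison is conditional on finding a suitable comparator, section 9.7.1 will describe treatment experience first, the one-year look-back is only the general rule, and final codes and definitions are left to the SAP. These points leave room for a remedy. They do not supply one, because the 365-day rule is fixed and nothing listed looks for earlier use of the same drug.

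Finally, 365 days is the only washout that the 12-month residency condition guarantees for everyone, and section 9.7 already raises precision concerns. That is a fair reason not to insist on first-ever use as the main definition regardless of numbers.

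**Conclusion.** The asymmetry holds. It follows from the 365-day same-substance rule, the index-date definition and the opening date of the study period, and no listed provision removes or measures it. Its effect on the hazard ratios cannot be sized or signed from the protocol and may differ by outcome. Under the assumptions shown, a true ratio of 1 could read anywhere from 0.83 to 1.25 if restarter risk differed throughout follow-up, and about 1.01 to 1.02 (s = 20% to 30%) if a halved risk were confined to the first six months of five years.

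Two further inferences should be resisted. One is that the bias cannot be separated from a drug effect at all: restarters can be flagged and analysed apart as far as the registers reach back. The other is that first-ever use makes the arms equivalent: it removes recorded same-drug re-exposure, not differences in earlier exposure to other drugs. The point is worth acting on because the check is cheap and the comparability assessment is incomplete without it.

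**What to change.** - In sections 9.1 and 9.2.1, flag any recorded dispensing or administration of the index substance before the index date over all available look-back, as is already done for other JAK inhibitors.
- In section 9.7.1, report the restarter share for each cohort as part of the comparability assessment.
- In sections 9.7.2 and 9.7.2.1, run every comparative analysis under both the first-ever-use and the 365-day definitions. Make first-ever use the main definition if comparator numbers allow, and otherwise a prespecified sensitivity analysis. Settle the choice on cohort counts, before outcomes are compared.

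The cost is protocol and SAP wording and a change to the cohort code. No new data source is needed, and only date and substance are required, so the missing dose information in Danish treatment codes is no obstacle. The first-ever-user analysis will have fewer comparator patients, by a number that cannot be given while the study-size inputs are redacted; upadacitinib numbers should hardly change. Look-back length will vary by person, so report its distribution by cohort and describe the group as having no recorded earlier use.

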## 9.2. Setting

### 9.2.1. Source Population, Study Population and Study Cohort

The *source population* will be all individuals with at least one diagnosis of AD (ICD-10 code L20) as registered in the Danish and Swedish patient registers since 1998 (the year when ICD-10 was fully implemented in both countries).

To be eligible for inclusion into the *study population* and the *study cohorts* individuals must:

- have a recorded diagnosis of AD
- have at least one dispensed prescription/administration of upadacitinib or one of the select systemic AD treatments within 12 months from the AD diagnosis during the *study period* (see definition in Section 9.2.2. )
- be a *new user* of either upadacitinib or one of the select systemic AD treatments at *index date*
- be  $\geq 12$  years old at the *index date*
- have at least 12 months' continuous residency in the respective country (Denmark or Sweden) prior to the *index date*
- For the potential comparator cohorts, have at least one dispensed prescription/administration of another systemic AD treatment before *index date*

The following exclusion criteria apply to the study population:

- Individuals who used other JAK inhibitors (e.g. tofacitinib, baricitinib, abrocitinib) at any time (all available lookback time) before the *index date* will be excluded

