### 9.3.2. Outcomes

The outcomes will be first event of:

- Malignancy (excluding NMSC), including malignancy by type
- NMSC
- MACE
- VTE

- Serious (in-patient) infections (incl. OI)
- HZ
- EH/KVE
- Active TB
- GI perforations
- DILI
- Fractures
- All-cause mortality

Incident malignancies will be identified via the linked national cancer registers and the national patient registers in each country. The other outcomes will be captured through inpatient and specialist outpatient diagnoses, as reflected in the national patient registers, in each country. Details on the coding, definitions, history exclusion look-back periods and source of the outcomes are listed in Annex 3. Additional Information, [Table 3.3](#).

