### **9.3.3. Baseline Variables**

In addition to exposures and outcomes, other variables that are recorded in the national registers will be included in this study. These variables will include demographic and socioeconomic measures (e.g., age, sex, region of residency, education, income, occupation, country of origin), proxy measures for lifestyle factors (e.g., smoking, alcohol use), comorbidities, past and present medication use, and prior medical procedures. As a proxy measure of disease severity, healthcare utilization within one year before cohort entry will be studied.

A list of baseline variables is presented in [Table 1](#). In general, one-year look-back period prior to *index date* will be used for medication use and disease severity proxies and five years for all the other variables.

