**Table 1 Baseline Variables**

Data type	Description
Demographics and socioeconomics	Age Sex Education Income Occupation Region of residency
Lifestyle factors	Smoking (identified through proxies) Alcohol use (identified through proxies)
Medical history within 5 years prior to index date	Asthma Obesity Hypertension Hyperlipidemia Diabetes Myocardial infarction Stroke Peripheral vascular disease Rheumatoid arthritis Depression Anxiety Insomnia Chronic obstructive pulmonary disease (COPD) Moderate hepatic impairment Serious infection Active TB Atherosclerotic cardiovascular disease Malignancy Chronic infection with hepatitis B virus (HBV) or hepatitis C virus (HCV) Severe renal impairment Endogenous uveitis Nephrotic syndrome Transplantation (organ/bone marrow) Psoriasis Crohn's disease Ulcerative colitis Celiac disease Acute lymphocytic leukemia (ALL) Systemic lupus erythematosus (SLE) Polymyositis and dermatomyositis Pemphigus Polyarteritis nodosa Autoimmune hemolytic anemia Chronic Idiopathic (Immune) Thrombocytopenic Purpura Polyarticular Severe Active Juvenile Idiopathic Arthritis External Otitis Previous fracture
Medication use within 1 year prior to index date	Antihypertensives Lipid-lowering drugs Antidepressants Anxiolytic drugs Antipsychotics Insomnia medications

Use of AD treatments other than the ones being studied within 1 year prior to index date	Biologic Non-biologic systemics Phototherapy Topical agents
Healthcare utilization as proxies of AD severity within 1 year prior to index date	Number of AD inpatient days at baseline Number of AD outpatient visits at baseline Number of non-AD inpatient days at baseline Number of non-AD outpatient visits at baseline

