### **9.7.3. Missing data**

Within each data source, if information on a particular variable is available, individuals will be assumed not to have the factor if there is no evidence for its presence (i.e., values for variables used in a given data source will not be considered missing). The only exception to this principle will be in the situation where "missing" is one of the possible values recorded for the variable, in which case the value as listed within the data source will be retained in the analysis as one of the possible values (e.g., a variable can be "yes" "no" or "missing"). Missing data will not be imputed but treated as missing.

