**Table 3.3. Outcomes**

Diagnosis Codes (ICD-O-3 and ICD-10)	Register	History exclusion look-back period	Description
Malignancies excluding NMSC			
[REDACTED]	Cancer/Patient	5 years	
Non-melanoma skin cancer (NMSC)			
[REDACTED]	Cancer/Patient	5 years	
MACE (non-fatal MI, non-fatal stroke, CV death)			
[REDACTED]	Patient, Cause of Death		
Serious infections (any hospital-treated infections, including opportunistic infections)			
[REDACTED]	Patient	1 year	Respiratory tract infections. In-patient only
[REDACTED]	Patient		Infections of the gastrointestinal tract* In-patient only
[REDACTED]	Patient		Urinary tract infection
[REDACTED]	Patient		Infections of the skin and subcutaneous tissue In-patient only
[REDACTED]	Patient		Other infections In-patient only
Venous thromboembolic event (VTE)			
[REDACTED]	Patient	5 years	
Herpes zoster (HZ)			
[REDACTED]	Patient	1 year	
Eczema herpeticum (EH)/Kaposi's varicelliform eruption (KVE)			
[REDACTED]	Patient	1 years	
Active tuberculosis (TB)			

Diagnosis Codes (ICD-O-3 and ICD-10)	Register	History exclusion look-back period	Description
[REDACTED]	Patient	5 years	J04AK05 (bedaquiline)J04AK01 (pyrazinamide)J04AK02 (ethambutol)
Gastrointestinal (GI) perforations			
[REDACTED]	Patient	5 years	
Drug-induced liver injury (DILI)			
[REDACTED]	Patient	5 years	Toxic liver disease
All-cause mortality			
[REDACTED]	Cause of Death		All deaths in Cause of Death Register
Fractures			
[REDACTED]	Patient	5 years

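### Twelve months' required residency cannot support the 5-year look-back used for medical history and for seven outcome exclusions, and no planned analysis tests the gap

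*Protocol*

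**What the plan says.** - **Eligibility (section 9.2.1).** Each entrant must "have at least 12 months' continuous residency in the respective country" before index. Only the potential comparator cohorts must also have an earlier dispensing or administration of another systemic AD treatment.
- **Covariates (section 9.3.3, Table 1).** Medication use and severity proxies have a one-year window; the protocol keeps "five years for all the other variables". Table 1 heads its comorbidity list "Medical history within 5 years prior to" index. That list includes hepatic impairment, HBV/HCV and renal impairment, which define secondary-objective strata.
- **Outcomes (section 9.3.2, Table 3.3).** "The outcomes will be first event of" each listed type. The column "History exclusion look-back period" gives 5 years for malignancy excluding NMSC, NMSC, VTE, active TB, GI perforation, DILI and fractures. It gives 1 year for serious infections, HZ and EH/KVE, and shows no period for MACE.
- **Absent records (section 9.7.3).** "individuals will be assumed not to have the factor if there is no evidence for its presence".
- **Migrants.** Section 9.4 notes that lifelong register coverage does not extend to migrants. Neither the planned sensitivity analyses (section 9.7.2.1) nor the limitations (section 9.9) mention a look-back cut short by immigration.

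**The concern.** The 12-month residency rule fits the 12-month new-user wash-out in section 9.1 and the one-year look-backs. It does not fit the 5-year ones. A person who immigrated 1 to under 5 years before index is eligible, yet part of the 5-year window lies before the registers could record that person.

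Two things are at stake. First, the seven 5-year exclusions cannot be applied in full to these entrants. An event before immigration is invisible, and a code for it after index could be taken as a first event. This bears directly on the primary objective, because section 9.7.1 reports crude incidence rates in upadacitinib users, where no comparator offsets such an error. Second, 5-year comorbidities may be under-recorded in the same people. Those comorbidities feed the baseline tables, the propensity scores used to judge comparability, and the strata by hepatic, viral hepatitis and renal history.

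**Working it through.** The protocol states no figure to reproduce here, and the study-size section is redacted. Three checks are possible.

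**1. Share of the 5-year window that cannot be seen.** Inputs: required residency of 12 months (section 9.2.1) and a look-back of 5 years (section 9.3.3, Table 1, Table 3.3). With r years of residency at index, the unseen share is max(0, 5 − r)/5.

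| Residency at index | Unseen share |
|---|---|
| 1 year | 4/5 = 80% |
| 2 years | 3/5 = 60% |
| 3 years | 2/5 = 40% |
| 4 years | 1/5 = 20% |
| 5 years or more | 0% |

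If residency were uniform over 1 to 5 years (an assumption), the mean would be 40%. Section 9.7.3 does not soften this. Its rule is written for a variable within a data source, not for the time a person was covered, so years before immigration are read as free of the condition.

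**2. Protection from the malignancy lag.** Section 9.3.2 treats malignancies and NMSC coded during the lag as history under the ITT and modified ITT definitions. The shortest observed event-free period is residency plus lag:
- main analysis: 12 + 12 = 24 months
- 6-month lag: 12 + 6 = 18 months
- 0-month lag: 12 + 0 = 12 months

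All three are shorter than 60 months. No lag is given for VTE, active TB, GI perforation, DILI or fractures, where the minimum is 12 months.

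**3. Possible size.** Relative inflation of a crude rate = f × h × q / IR. Here f is the share of the cohort resident 1 to under 5 years; h is the share of those with a prior event in the unseen part of the window; q is the yearly probability that it is first coded after index; and IR is the true rate. The protocol gives none of these, so every value below is an assumption.

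| f | h | q | False events per 1,000 PY | IR = 5 per 1,000 PY | IR = 1 per 1,000 PY |
|---|---|---|---|---|---|
| 1% | 1% | 0.1 | 0.01 | 0.2% | 1% |
| 5% | 3% | 0.3 | 0.45 | 9% | 45% |
| 10% | 3% | 0.3 | 0.90 | 18% | 90% |

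The range runs from negligible to large, and rarer outcomes are the more exposed. The table shows only that the size is undetermined; no row is an estimate.

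**The case against.** A reader might infer that recent immigrants' existing disease will be counted as incident, so that the seven rates are biased upward by a known amount. The documents do not support that. A false first event needs a prior condition in the unseen years, no code during at least 12 months of residency, and a first code after index. Every entrant already has an AD diagnosis in a patient register, so a condition active enough to be coded later may well have been coded before index. VTE, GI perforation, DILI and fractures are largely acute. Whether a history-type code could trigger them cannot be judged, because the codes are redacted. Events more than 5 years old pass the exclusion for lifelong residents too and are not an extra error.

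A reader might also infer that eligibility itself must become 5 years for the affected outcomes. That is debatable. It would remove recent immigrants from the main TB analysis, make populations differ by outcome, and leave the 5-year covariates incomplete for outcomes kept at 12 months.

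Finally, Annex 3 says its tables are not final, and section 9.7.2.1 leaves sensitivity-analysis details to the SAP. But the residency rule and the reading of absent records are fixed in the protocol, and together they produce the gap whatever codes are chosen.

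These points limit the consequence and the remedy. They do not remove the mismatch.

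**Conclusion.** The mismatch stands. For entrants resident 1 to under 5 years, the stated 5-year exclusion and covariate window cannot be observed in full: 80% is unseen at 1 year of residency, 20% at 4 years. False first events and under-recorded history are possible, not certain. Malignancy and NMSC are partly protected in the main analysis and less so in the 0- and 6-month lag analyses. Outcomes with a 1-year look-back are affected only through the covariates.

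The error may differ between cohorts. Someone treated only abroad has no visible earlier systemic treatment, so that person can enter the upadacitinib cohort but not a comparator cohort until such a treatment is recorded in the country. Other things equal, this favours short-residency entrants in the upadacitinib cohort. Country of origin, named in the text of section 9.3.3 though not in Table 1, would allow part of any imbalance to be examined. Neither the size of the bias nor its effect on a hazard ratio can be derived from the protocol.

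**What to change.** 1. In section 9.7.2.1, prespecify a sensitivity analysis of the crude incidence rates and the comparative models, for all outcomes, restricted to entrants with at least 5 years' continuous residency before index. In that run the unseen share of the window is 0%.
2. Report the number of entrants resident 1 to under 5 years, by cohort. This gives the missing f and shows whether it differs between cohorts.
3. State the truncated look-back as a limitation in section 9.9.

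The cost is one extra run; migration data are already to be obtained from the population registers (section 9.4). The restricted run loses recent immigrants, which matters most for TB, so the 12-month version should stay alongside it. A difference between the two may reflect a genuinely different risk in recent immigrants as well as misclassification, and should be read with that in mind.
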